3.4.4 Pre-hospital Discharge/Wound Check and 3-month Follow-up

As the analysis of secondary endpoint 2 is complete, additional LV pacing threshold testing using the novel pacing vectors is optional at the pre-hospital discharge/wound check and the 3 month post-implant follow-up. The pre-hospital discharge/wound check visit occurs after successful device system implantation and either prior to the subject's discharge from the hospital or at a routine wound check visit (occurring no later than 45 days after implantation). Three (3) months (\pm 30 days) after implantation, subjects return to the investigational site for an in-office assessment of their implanted system. For both visits the CRT-D system should be assessed.

The following requirements have to be fulfilled and the data have to be documented on the Pre-hospital Discharge/Wound Check eCRF or 3-month Follow-up eCRF, respectively:

1. Standard Sentus QP lead evaluation:
 - Determine LV lead impedance
 - Determine LV lead R-wave sensing
 - Determine LV pacing threshold at 0.4 ms pulse width for the pacing vector programmed at the beginning of the device interrogation
2. Plexa ICD lead evaluation from implant procedure (if Plexa ICD lead is implanted with initial Sentus QP lead):
 - Determine Plexa ICD lead R-wave sensing amplitude
 - Determine Plexa ICD lead pacing threshold at 0.4 ms pulse width

- Determine Plexa ICD lead pacing impedance
 - Determine Plexa ICD lead shock impedance
3. Novel pacing vector evaluation, if performed
 - Measure the LV pacing threshold with 0.4 ms pulse width
 4. Check the activation of the recommended device settings (Section 3.2.4).
 5. Screen/Enroll subject for MPP Sub-Study if prior HF Hospitalization event (3-month Follow-up Only) → Refer to Protocol Section 11
 6. Device programming and settings at end of follow-up.
 7. At pre-hospital discharge or wound check, register the subject in the Home Monitoring Service Center.
 8. Store the electronic procedure data (including final device settings, measurements, episodes) of the BIOTRONIK programmer on an appropriate USB flash drive.
 9. Complete the electronic Pre-hospital Discharge/Wound Check or 3-month Follow-up eCRF.
 10. Document any reportable adverse event (e.g. phrenic nerve stimulation, high LV pacing threshold, etc.) or device complaint by using the respective eCRF. Please adhere to the reporting timelines listed in Section 10.2.

Please note: Phrenic nerve stimulation occurring during the left ventricular threshold test and not leading to any serious medical symptoms are not considered adverse events and thus do not need to be reported in an Adverse Event eCRF.

In order to support the CRT responder assessment for enrollment into the MPP sub-study, the MPP feature should not be programmed ON prior to the 6-month follow-up (or the 3-month follow-up for subjects consented for the MPP sub-study due to a HF hospitalization event).

3.4.5 6-month Follow-up and 12-month Follow-up

Six (6) months (\pm 45 days) and 12 months (\pm 45 days) after implantation, subjects return to the investigational site for an in-office assessment of their implanted system.

The following data should be collected:

1. Standard Sentus QP lead evaluation:
 - Determine LV lead impedance
 - Determine LV lead R-wave sensing amplitude
 - Determine the LV pacing threshold at 0.4 ms pulse width for the

- programmed pacing vector
2. Plexa ICD lead evaluation from implant procedure (if Plexa ICD lead is implanted with initial Sentus QP lead):
 - Determine Plexa ICD lead R-wave sensing amplitude
 - Determine Plexa ICD lead pacing threshold at 0.4 ms pulse width
 - Determine Plexa ICD lead pacing impedance
 - Determine Plexa ICD lead shock impedance
 3. Screen/Enroll Subject for MPP Sub-Study (6-Month Follow-up Only) → Refer to Protocol Section 11
 4. Device programming and settings at end of follow-up.
 5. Store the electronic procedure data (including final device settings, measurements, episodes) of the BIOTRONIK programmer on an appropriate USB flash drive.
 6. Complete the appropriate Follow-Up eCRF.
 7. Document any reportable adverse event (e.g. phrenic nerve stimulation, high LV pacing threshold, etc.), or device complaint by using the respective eCRF. Please adhere to the reporting timelines listed in Section 10.2.

Any subject not enrolled into the MPP sub-study may only have the MPP feature activated at the investigator's discretion any time after the 6-Month follow-up if the subject is determined by the investigator to be a non-responder.

3.4.6 Additional Visits Required Every 6 Months to 60 Months

After completion of the 12-month follow-up visit, subjects enrolled at U.S. study sites will be followed every 6 months until 60 months post-implant. For subjects utilizing BIOTRONIK Home Monitoring[®], study sites will have the option to substitute a BIOTRONIK Home Monitoring[®] evaluation for up to every other of these additional visits. BIOTRONIK Home Monitoring[®] evaluations will be accompanied by a phone assessment that is designed to document clinical signs and symptoms that identify a potential reportable adverse event, or device complaint. The phone assessment should occur within 7 days of the date of the BIOTRONIK Home Monitoring[®] report. Subjects utilizing BIOTRONIK Home Monitoring[®] assessments are still expected to be evaluated in-office at least once per year.

The data collected for these additional visits is the same as required for the 6 and 12 month evaluations (Section 3.4.5). For BIOTRONIK Home Monitoring[®] evaluations, a Summary Report created in the Home Monitoring Service Center will be used to store the required electronic procedure data.

3.4.7 Interim Follow-up

Interim follow-ups may occur anytime during the clinical investigation; however, those interim evaluations in support of lead or system related adverse events or system revisions may be collected in the clinical investigation. Interim follow-ups can be visits scheduled by physicians according to clinical routine, visits scheduled by the physician due to BIOTRONIK Home Monitoring® alerts or trends, or visits initiated by the subject.

3.4.7.1 Adverse event related interim follow-up

For interim follow-ups related to an adverse event, the data collected on the Interim Follow-up eCRF is the same as the 6 and 12 month evaluations (Section 3.4.50).

3.4.7.2 System Revision

For interim evaluations that involve a system revision (even if the Sentus QP lead is not directly affected), the following data is required:

1. Implantation procedure information (date of intervention, information about new implanted devices).
2. Revised device (manufacturer, model, serial number).
3. Sentus QP lead measurements during procedure:
 - Determine LV lead impedance
 - Determine LV lead R-wave sensing amplitudes
 - Determine LV pacing threshold at 0.4 ms pulse width for the pacing vector programmed at the end of intervention.
4. Device programming and settings at end of intervention.
5. Plexa ICD lead measurements during procedure (if Plexa ICD lead is implanted with initial Sentus QP lead):
 - Determine Plexa ICD lead R-wave sensing amplitude
 - Determine Plexa ICD lead pacing threshold at 0.4 ms pulse width
 - Determine Plexa ICD lead pacing impedance
 - Determine Plexa ICD lead shock impedance
6. Store the electronic procedure data (including final device settings, measurements, episodes) of the BIOTRONIK programmer on an appropriate USB flash drive.
7. Complete the electronic System Revision eCRF.
8. Document any reportable adverse event (e.g. phrenic nerve stimulation, high LV pacing threshold, etc.), or device complaint during the procedure by using the respective eCRF. Please adhere to the reporting timelines listed in

Section 10.2.

Please note:

1. If the Sentus QP lead is explanted and the subject does not receive a new Sentus QP lead, the subject will be withdrawn from the clinical investigation.
2. If the Sentus QP lead is replaced with another Sentus QP lead, the subject will continue participation in the clinical investigation based on the original implantation date and visit schedule.
3. The subject will continue participation and time schedule will be unchanged if any other lead is replaced or if the CRT-D is replaced (even if replacement CRT-D is not BIOTRONIK).
4. Please notice, whenever possible, BIOTRONIK devices that are explanted must be returned to BIOTRONIK, Inc. for analysis.

3.4.8 Study Termination

The Study Termination eCRF must be completed to determine the end date and reason for study termination of the individual subject. The expected study termination for all subjects should not be earlier than the 60 month follow-up visit. Reasons for early study termination are described in Section 3.5.2.

3.5 Study Participation Expectations

3.5.1 Point of Enrollment

A subject is considered enrolled in the QP ExCELS study upon signing the Informed Consent Form and meeting the inclusion/exclusion criteria at time of consent.

3.5.2 Reasons for Study Termination

Once a subject is enrolled and successfully implanted, every effort should be made to continue to follow the subject in the clinical investigation. However, it is inevitable that some subjects will decline to participate further, change geographic location, or become non-compliant with the visit schedule.

3.5.2.1 No implant attempt

If a Sentus QP implantation was planned but not performed or the implant procedure was initiated but the Sentus QP did not come in contact with the subject, the subject is exited. The reason for study termination must be provided.

3.5.2.2 Unsuccessful implant

If a Sentus QP lead came in contact with the subject but could not be implanted, an adverse event or device complaint should be completed and the subject exited. Data for subjects that have a Sentus related adverse event according to the listing provided in Section 6 will be included in analysis.

3.5.2.3 Withdrawal of subject consent

Subjects may withdraw their consent for study participation at any time without stating the reason and without any unfavorable consequences. All data, which are collected until the date of withdrawal will be used for analysis. A Study Termination eCRF has to be completed by the investigator in which the reasons for withdrawal should be documented if willingly provided by the subject.

3.5.2.4 Subject death

In the event of subject death during study participation, personnel at the investigational site are requested to notify BIOTRONIK, Inc. immediately by completing an Adverse Event eCRF (if applicable) and a Study Termination eCRF.

The following information will be required for any subject death:

- Death certificate, death report signed by the investigator, or relevant medical records that include:
 - Date of death
 - Primary cause of death
 - Any other circumstances surrounding the death
 - Whether death was device or procedure related
- Sentus QP lead return status, if available

Whenever possible, devices that are explanted must be returned to BIOTRONIK, Inc. for analysis.

3.5.2.5 Sentus QP lead extraction

Any subject who has the Sentus QP lead explanted and not replaced with another Sentus QP lead will be withdrawn from the clinical investigation. After documentation of the system revision procedure (see Section 3.4.7.2), a Study Termination eCRF should be completed.

Whenever possible, devices that are explanted must be returned to BIOTRONIK, Inc. for analysis.

3.5.2.6 Lost to follow-up

Subjects lost to follow-up are those for whom contact is lost despite the investigator's best efforts to locate the subject. Study sites should attempt to contact these subjects in order to maintain study visit compliance and all contact attempts should be documented. At a minimum, the site should make two attempts to contact the subject by phone and one attempt by certified mail.

In the event the subject cannot be contacted using the above methods, the subject is terminated from the clinical investigation by completing a Study Termination eCRF.

3.5.3 Date of Study Termination

The expected study termination for all subjects should not be earlier than the 60 month follow-up visit.

For all early study terminations, the following rules apply:

- In case of withdrawal of consent, date of study termination is the date of withdrawal of consent.
- In case of subject death, the date of study termination is the date of death.
- If subject is lost to follow-up, date of termination is the date of last documented contact with the subject.
- If a Sentus QP implantation was planned but was never attempted, the date of termination is the date of decision not to implant.
- If a Sentus QP implantation was initiated but not completed and the Sentus QP did not come in contact with the subject, date of unsuccessful implantation is date of study termination.
- If an attempt to implant Sentus QP lead was made and lead came in contact with subject but implantation was ultimately not successful, date of study termination is date of unsuccessful implantation.
- If the Sentus QP is explanted and not replaced with another Sentus QP, the date of study termination is the date the lead is explanted.

Study related procedures and documentation should end at the day of study termination for the respective subject.

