3.4.3 Implantation

Implantation occurs after enrollment of the subject.

At implantation, the following procedures/data are required:

1. Implanted devices (manufacturer, model, serial number).
2. Implantation procedure information (see Section 3.2.3).
3. Sentus QP lead implant success.
4. Approximate vessel diameter at Sentus QP lead tip (at final lead position, when this information is available from a routine venogram performed during implant).
5. Activation of the recommended device settings as listed in Section 3.2.4.
6. Sentus QP lead evaluation from implant procedure:
 - Determine LV lead impedance
 - Determine LV mean R-wave sensing amplitudes
 - Determine LV pacing threshold at 0.4 ms pulse width for the pacing vector programmed at the end of implantation
7. Plexa ICD lead evaluation from implant procedure (if Plexa ICD lead is implanted with initial Sentus QP lead):
 - Determine Plexa ICD lead R-wave sensing amplitude
 - Determine Plexa ICD lead pacing threshold at 0.4 ms pulse width
 - Determine Plexa ICD lead pacing impedance
 - Determine Plexa ICD lead shock impedance
8. Device programming and settings at end of implantation procedure.
9. Store the electronic procedure data (including final device settings, measurements, episodes) of the BIOTRONIK programmer on an appropriate USB flash drive.

10. Complete the Implantation eCRF using data collected during implant and information from the end of procedure device evaluation.
11. Document any reportable adverse event (e.g. phrenic nerve stimulation, high LV pacing threshold, etc.) or device complaint during the procedure by using the respective eCRF. Please adhere to the reporting timelines listed in Section 10.2.

Please note:

1. If a Sentus QP implantation was planned but not performed or the implant procedure was initiated but the Sentus QP lead did not come in contact with the subject, the subject will be exited from the clinical investigation using a Study Termination eCRF.
2. If an attempt to implant a Sentus QP lead was made and the lead came in contact with subject but implantation was not successful, reportable adverse events related to the implant attempt will be collected and the subject will be exited from the clinical investigation using a Study Termination eCRF.

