6.2 Reporting Adverse Events

The investigator shall report to the sponsor, by completing the appropriate eCRF, the following types of events:

- all adverse events related to or possibly related to
 - investigational device
 - implanted system
- any major adverse events related to procedures involved with implanting, using, or testing the investigational device (see examples in Section 6.3 and definitions in Appendix A: Definition of Terms)
- any adverse device effects, regardless of severity and including both previously reported and unanticipated adverse events
- (MPP Sub-Study Only, see Section 11.5.4) any cardiovascular hospitalizations and any other hospitalizations in which cardiovascular symptoms occur on or before the date of the 12-Month follow-up
- (MPP Sub-Study Only, see Section 11.5.4) all adverse events that require additional invasive intervention to resolve, specifically related to the MPP feature of the CRT-D. These adverse events include any software issues related to MPP programming for any adverse event that occurs while MPP is enabled and that may be attributed to the use of the MPP feature.

(Please note: Phrenic nerve stimulation is an expected event during left ventricular threshold testing. As the Sentus QP lead allows for measurements in up to 12 different vectors, phrenic nerve stimulation might be a common observation in this study. Therefore phrenic nerve stimulation during threshold testing is only considered a reportable adverse event if serious medical symptoms occur.

Events will be reported on an Adverse Event eCRF or a Device Complaint eCRF, as appropriate. Events should be reported as information is available, even if this results in an incomplete eCRF. The investigator must follow-up all ongoing reportable events either as long as the subject participates in the clinical investigation, the clinical investigation is terminated, or until the event has been resolved, whatever comes first.

The investigator must characterize each event by a single primary diagnosis. The primary diagnosis may describe an event consisting of several clinically recognizable features, symptoms or secondary diagnoses. Note: The observed symptoms and secondary diagnoses must be properly documented in the respective eCRF.

Multiple events may occur simultaneously in one subject. For each medically independent event with a primary diagnosis an individual report must be provided.

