- Pneumothorax directly associated with the Sentus QP lead
- Cardiac perforation with or without tamponade caused by the Sentus QP lead
- Coronary sinus dissections directly caused by the Sentus QP lead (e.g., dissections caused by lead delivery device are excluded)

Finally, subject deaths resulting from a Sentus QP lead-related AE will be included in the primary endpoint analysis.

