	<0.01 ³¹	Peripheral nerve injury
	<0.01 ³¹	AV-fistula
Not known Frequency not assessable on the basis of the available data		Allergic reaction to dexamethasone acetate, bleeding ³² , brachial plexus injury ³² , device migration ^{30,41} , diaphragmatic stimulation ³² , discomfort, erosion, exit block ³² , failure to insulate set screw ³² , hemoptysis ³² , injury to vagus nerve ³² , lead malpositioning ³² , lead microdislocation ³² , local tissue reaction ³⁰ , muscle stimulation ³⁰ , nerve stimulation (general) ³⁰ , myocardial lesion ³⁰ , pocket seroma ³² , subclavian artery puncture ³² , higher x-ray load due to extended fluoroscopy times ³⁴ , failing of shock test ⁴⁰ , injury due to implantation accessories ^{42,44}

Table 16b: Expected Postoperative Events

Frequency	Percentage (%)	Risk
	9.7 ²⁰ -37 ²³	Lead failure ^{20,22,23}
Very frequent >1 out of 10 patients	2.9 ⁷ –25.4 ²⁴	Inappropriate shocks ^{7,24,25,54}
	Up to 13 ²⁹	Device explantation (manufacturers` advisory: 4% ²⁹ , electronic failure: 2% ²⁹ , housing defects: 1% ²⁹)
	0.3 ¹ – 13.6 ⁴	Phrenic nerve stimulation
	12 ^{6,21}	Lead dysfunction
	1.2 ¹⁹ –10.6 ²	Lead dislodgement
Frequent 1 to 10 patients out of 100	1.7 ² – 9.5 ²	Formation of clinical significant hematomas
	7.6 ¹⁵ – 9.5 ¹	Hematoma ^{1,3,15,16,17}
	7 ⁴⁶	Subclavian vein occlusion ≥ 75%
	0.1 ⁵ – 7 ¹	Infections ^{1,5,14} (CRT-D related: 1.9 ^{1,4,13} - 1.9% ^{1,4} ; in-hospital infections: 0.7% ¹² ; infections after replacement: 1.9% ¹³)
	0.1 – 4.2 ⁶⁰	Lead fracture
	1.6 ⁷ – 3.9 ⁴	Elevated pacing threshold/ loss of capture/ failure to capture
	2.4 ³⁰	Aggregate perforation

	3.4 ³⁰	Pocket erosion
	0 ² – 1.5 ⁷	Mortality within 30 days after implant (0.4% related to implant procedure ⁷)
	1.5 ³⁰	Premature depletion of battery
	1.4 ⁷	Diaphragmatic muscular stimulation
	0.3 ² – 1.3 ⁵	Lead perforation
	1.3 ¹	Pericarditis requiring anti-inflammatory agents
	0.05 ⁷ – 1,2 ^{12,57,61}	Pneumothorax
	0.9 ¹	High LV threshold
	0.7 ⁵	Oversensing
	0.6 ⁷	Discomfort
	0.6 ⁷	Pain at device pocket
	0.6 ¹	Pericardial effusion requiring intervention
	0.6 ⁷	Seroma
	0.6 ⁷	Shoulder pain
	0.5 ⁴	Lead conductor fracture
	0.5 ³⁰	M. pectoralis tremor
	0.3 ⁵ – 0.5 ¹⁸	Post-operative perforation
	0.7 ⁵⁴	Thrombosis of brachial, subclavian or jugular veins
	0.3 ¹²	Acute renal failure requiring hemodialysis
	0.3 ¹	Ipsilateral venous thrombosis
	0.3 ⁷	System- or lead-related arrhythmia
	0.2 ⁴	Elevated lead impedance
	0.2 ⁶³	Site pain
	0.2 ⁵⁴	Thrombosis of deep femoral vein

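### Subjects with a failed lead attempt or an unreplaced explant exit on the procedure day, with no reliable provision to capture anticipated harm that appears later or the outcome of an event still open

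*Combined protocol and SAP*

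**What the plan says.** **Exit rules.** For a failed attempt in which the lead contacted the subject, Section 3.5.3 states: "implantation was ultimately not successful, date of study termination is date of unsuccessful implantation". For an explant without Sentus QP replacement: "the date of study termination is the date the lead is explanted". For every subject: "Study related procedures and documentation should end at the day of study termination for the respective subject". Sections 3.5.2.2, 3.5.2.5 and 3.4.7.2 confirm the exit.

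**Open events and deaths.** Section 6.2 has the investigator follow an ongoing reportable event "as long as the subject participates in the clinical investigation, the clinical investigation is terminated, or until the event has been resolved, whatever comes first". Section 3.5.2.4 requests notification of deaths that occur during participation.

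**What the plan means to capture.** For a failed attempt with lead contact, Section 3.4.3 says that "reportable adverse events related to the implant attempt will be collected and the subject will be exited from the clinical investigation". Section 3.5.2.2 puts Sentus-related adverse events of such subjects into the analysis, and Section 2.3.2 admits implants that failed because of a lead complication to primary endpoint 1. Sections 6.6.1 and 6.6.2 count lead-caused perforation and coronary sinus dissection and lead-associated pneumothorax, and both say that "subject deaths resulting from a Sentus QP lead-related AE will be included in the primary endpoint analysis".

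**Who is not affected.** A failed attempt followed by a successful repeat stays in the study (Section 3.4.3), as does an explant replaced with another Sentus QP (Section 3.4.7.2).

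**The concern.** The harms that the endpoint definitions list need not be apparent on the day of the procedure. A perforation or tamponade can declare itself later, and a death can follow later still. Section 6.1.4 makes an overnight hospital stay or death a criterion of seriousness, and neither need be known at day 0. Under the exit rules, a subject whose vein or heart was injured in a failed attempt or an extraction is already out of the study by then. An event recorded on day 0 can be left without an outcome.

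Section 12.3 values the EchoCRT data because consent before implant secures reporting of events at implant and immediately afterwards. This study also enrols before implant, but gives up the second part for these subjects. At stake is the completeness of what reaches the Clinical Events Committee and the safety reports, for people exposed to lead handling and then observed for no time afterwards.

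**Working it through.** **1. Rules set side by side.**

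| Situation after exit | Rule that applies | Route into the data |
|---|---|---|
| Harm recognised on the procedure day | 3.4.3, 3.5.2.2, 2.3.2 | Yes |
| Event open at exit | 6.2: follow-up stops with participation | Outcome not secured |
| New anticipated harm after exit | 3.4.3 gives no time limit; 3.5.3 ends documentation at exit | Conflict; no contact planned |
| Death after exit | 3.5.2.4 covers deaths during participation | None stated, although 6.6.1 and 6.6.2 count lead-related deaths |
| Unanticipated device effect after exit | 6.4: the clock starts when the investigator learns of it | Yes, if learned of |

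No section sets a safety contact, a vital-status check or an adverse event window after exit.

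**2. How many subjects.**

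- *This lead.* Section 2.3.1 defines the pre-market cohort to include implant attempts. Section 1.4 gives its size as 299. Section 1.4.2 reports 286 evaluable for primary endpoint 2, none of them an unsuccessful implant. Failed attempts are therefore at most 299 − 286 = 13, and 13/299 = 4.3%. Some of the 13 may be other early exits. Scaled to the planned U.S. enrolment: 1,754 × 13/299 ≈ 76.
- *Predecessor lead.* Section 12.1 reports 144 attempts and 131 successes: 144 − 131 = 13 failures, and 13/144 = 9.0%. Scaled: 1,754 × 13/144 ≈ 158. The equal numerators are a coincidence.
- *Unreplaced explants* come on top. The documents give no count.

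**3. Expected events.** Assumption: Table 16b rates, which come from literature on implanted patients, also apply after a failed attempt.

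- Mortality related to the implant procedure, 0.4%: 76 × 0.004 = 0.3 deaths; 158 × 0.004 = 0.6.
- Post-operative perforation, 0.3% to 0.5%: 76 × 0.003 = 0.2 to 76 × 0.005 = 0.4; with 158 subjects, 0.5 to 0.8.

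Not all of these would be caused by the Sentus QP lead.

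**4. Effect on primary endpoint 1.** The plan's result reproduces: 271/279 = 97.1%, exact 95% interval 94.4% to 98.8%, one-sided p = 4 × 10⁻⁶ against 90%. The lower bound is the 2.5% quantile of Beta(x, n − x + 1) and must exceed 90.0%. The cohort holds 299 − 279 = 20 non-evaluable subjects. The documents do not say how many were failed attempts or explants, so a range is shown.

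| Assumption | Still met | Lost |
|---|---|---|
| All 20 added | 11 extra events: 280/299, bound 90.25% | 12 extra events: 279/299, bound 89.86% |
| Only subjects with events added | 10 extra events: 271/289, bound 90.33% | 11 extra events: 271/290, bound 89.96% |

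Reversal would need 11 or 12 missed events among 20 subjects. An explant for a listed complication already counts, once per subject (Section 2.2.1), so later harm in that subject would not move the rate.

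**5. Effect on primary endpoint 3.** Section 2.3.4 admits only successfully implanted subjects who complete the 60-month visit. Failed attempts and unreplaced explants are outside that population whatever is collected after exit.

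**The case against.** The strongest reply is that the plan already collects this harm. Section 3.4.3 sets no time limit on adverse events of the attempt. Section 6.3 makes an unsuccessful implant reportable in itself, and Section 5.1 sends serious procedure-related events to the committee. Section 3.5.3 says only that documentation should end. Section 6.4 is not limited to active participants.

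Part of this stands. A reader might infer that delayed harm is never collected and cannot reach FDA, and the documents do not support that. An investigator could still report under Section 3.4.3, and unanticipated device effects have a clear route. But Section 3.4.3 exits the subject in the same sentence, and Sections 3.5.3 and 6.2 point the other way. Appendix B treats its listed events, which include perforation, tamponade and dissection, as expected unless they differ in nature, severity or incidence. The unanticipated route therefore does not reliably catch them.

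On size, a reader might take the 635 − 576 = 59 enrolled but not implanted subjects in Section 1.4 (9.3%) and project about 163 of 1,754. That does not hold. Enrolment is counted at consent (Section 3.5.1), so the 59 can include subjects awaiting implant and subjects with no lead contact, and Section 2.4.3 keeps the latter out of the 1,754. All-cause 30-day mortality and infection rates would also overstate the loss: the same Table 16b row gives 0.4% for deaths related to the procedure, and infection is not a listed event in Table 7 or 8. The 9.0% belongs to a different, earlier lead.

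Finally, the Table 16b row "Mortality within 30 days after implant" is a literature incidence. It is not an observation period that this protocol adopts.

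**Conclusion.** The point holds as a conflict between sections with a practical consequence. Followed as written, Sections 3.5.3, 6.2 and 3.5.2.4 leave no reliable way to capture anticipated harm that emerges after the procedure day, or the outcome of an event open at exit. Sections 3.4.3, 3.5.2.2, 6.6.1 and 6.6.2 intend such harm to be collected and counted.

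The number affected is uncertain: up to about 76 U.S. subjects on this lead's pre-market experience, about 158 at the predecessor lead's failure rate, plus an unknown number of unreplaced explants. The lower figure assumes that the 299 follow the Section 2.3.1 definition, which includes attempts; Section 1.4 describes them more loosely as implanted. Expected lead-related events are few, below one for each of the two rates worked through.

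A reader might infer that the primary endpoint results are biased. The documents do not support that to any degree that matters: endpoint 1 was met with a wide margin, and endpoint 3 excludes these subjects by its population rule, which is a separate matter. The loss is in safety reporting and committee adjudication. Because the remedy is cheap, the change should be made.

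**What to change.** Reconcile Sections 3.4.3, 3.4.7.2, 3.5.2.2, 3.5.2.5, 3.5.3 and 6.2 as follows:

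- Any subject with lead contact and a failed implant, or with an explant not replaced by a Sentus QP, stays in the study for adverse event and vital-status collection only.
- Collection runs through one phone or chart contact at an interval the sponsor sets (30 days is one option), and until any open related event has resolved.
- The termination date becomes the date of that contact, or of resolution if later. Deaths in the interval then fall under Section 3.5.2.4.
- For these subjects, the end of device follow-up no longer ends the follow-up of an open event under Section 6.2.

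Section 3.4.6 already uses a phone assessment to detect reportable events, and it could be adapted. The cost is protocol and consent wording and one contact for a small share of subjects, with no device test or extra visit. Some of these subjects will have received a different lead, so the committee must adjudicate relatedness to the Sentus QP for anything reported.
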